This study evaluates the effect of a fractionated carbon dioxide laser on surgical scars of the face and neck over 12 months. Anyone with a surgical scar on the face and neck who has not had laser therapy may be eligible. The visits occur every three months for up to 12 months. Subjects will be randomly assigned to receive two high energy treatments or two low energy treatments. During the study visits, the scars will be photographed pre-treatment and the subject will complete a questionnaire to rate the scar. Three physicians will also evaluate the scar: one as a live assessment and the other two will evaluate the scars after each visit using photographs. Patients will receive their assigned treatment, obtain post-treatment instructions, and a diary to record redness, swelling, pain, itching, or other skin changes after treatment. Patients and raters will be blinded to which therapy level the patient receives until the 9-month visit (Visit #3) at which time patients will be unblinded and offered to have a third high energy treatment if in the high energy treatment group or to have two high energy treatments if in the low energy treatment group.

Study Timeline

The study will occur over 14 months. Our tentative timeline consists of recruitment and screening to occur in November 2016-September 2017. Study visits and data collection would occur between November 2016 and September 2017. Preliminary data analysis and publication of preliminary results would occur between August 2017 and March 2018. Final data analysis and publication would be between October 2018 and January 2019.

Introduction

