For the inclusion criteria, adult patients of all Fitzpatrick phototypes who have surgical scars of the head and neck will be screened for this study. There is no data to suggest that there is a difference in the appearance of older (more than 1 year old from the initial injury) and newer scars (at least 8 weeks after surgery) post-therapy. Most scars are fully mature at exactly 1 year from the date of the initial injury, so in the "older scar" cohort one may presume (in the absence of any confirmed findings in the medical literature) that any changes to these scars post-therapy will be an effect from the laser. The minimum age of the scar will be eight weeks from the initial surgery, as the scar has healed enough to determine if additional fine tuning may be helpful. In addition, standard practice is to allow a scar to heal for 8 weeks before laser treatment. Therefore subjects may be enrolled in the younger scar group if the scar is 8 weeks – 51 weeks from occurrence, and enrolled in the older scar group if the scar is 52 weeks or older from time of occurrence. We will aim to recruit 20 patients with old scars (10 of which will be in the high energy treatment group, and 10 of which will be in the low energy treatment group). In terms of statistical analysis, we will review whether there is a difference between the post-treatment measurements and appearance of older scars and newer scars. Patients must be able to understand the informed consent, willing to come to the office for treatments and capable of following post-treatment instructions.

In terms of exclusion criteria, patients who have had prior laser treatments to the face and neck, have a history of keloid formation, scars resulting from non-surgical etiologies (i.e. minor trauma), isotretinoin use in the last 6 months prior to study enrollment, and allergy to topical lidocaine will not be eligible for the study.

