A screening visit will occur whereby patients deemed appropriate for the study will have the segment of the scar with the most deformity defined for objective evaluation at each session. Baseline photographs of this area will be obtained and demographic data about the surgery that created the scar, associated wound healing complications, age of the scar, and the Fitzpatrick skin phototype will be collected. Randomization will occur at this visit and patients will receive their first treatment at this visit. Prior to treatment application, subjects will cleanse their face with a gentle cleanser, such as Cetaphil, provided in the office in order to remove all lotion, creams, make up, and sunscreen. An optional topical or local anesthetic medication will be offered to the subject and if desired by the subject will be applied to the treatment area approximately 20 minutes prior to the procedure. If the scar is deeper, an injection of numbing medicine (lidocaine with epinephrine) may be used as well. Once this time passes and the numbing medicine is working, the subject will be escorted to the procedure room. The treatment areas will be wiped clean of the numbing cream prior to the procedure. Just prior to the procedure, the subject's eyes will be covered with eye shields to protect their eyes. The treatment time may vary, but generally takes 10 minutes or less. During this time, subjects will hear the laser, which sounds like a bee buzzing, and will feel some warmth. Most patients report minimal discomfort during the procedure. There may be pinpoint bleeding, bruising, and crusting depending upon the area and extent of the treatment. After the treatment, patients will be provided with a 30-day diary to daily record treatment-related reactions: redness, swelling, pain, itching or color changes following treatment. If the subject has a history of recurrent fever blisters/cold sores on the lips or face, the subject will be offered a three day prescription for an antiviral medication that the subject can fill at the subject's pharmacy to prevent a recurrence since laser treatments may increase the chance of recurrent episodes. The subject would take one pill every twelve hours the day prior to treatment, on the treatment day, and the first day post-treatment. The subject or their insurance plan must cover the cost of the medication. This may delay the treatment to a later date within 30 days of the screening visit. If antibiotic/antiviral medications are needed, you and/or your insurance company will be responsible for covering this cost.

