
If a patient prefers not to have treatment at this visit, they will be asked to return to clinic for this first treatment within 30 days from the screening and randomization visit. Subjects will return for a second treatment 3 months later. With 10 min allotted for treatment, as well as completing the patient questionnaire (5-7 minutes), assessment of adverse events and updating medications and procedures, along with performing photographs (10 min) and having an evaluation by the blinded evaluator, the entire visit may take up to 30-40 min. The diary entries will take 5 minutes each day. Subjects will return again 3 months following the second treatment and will undergo the follow up photos and assessments. Subjects will be unblinded at the third visit to the treatment received and given three options. One option is to exit from the study. The second option is if the subject received the high energy laser treatments, the subject may elect one additional treatment that day. The third option is subjects with low energy treatments have the option to receive two high energy treatments at this visit and a subsequent visit. Those in the high energy group who receive the third optional high energy treatment will return in 3 months for an exit visit and follow-up assessment of the scar (photos, patient POSAS, and observer POSAS) and exit at visit #4. Those in the low energy group who elect the two high energy treatments will follow up in 3 months after Visit #3 for the final high energy treatment, photos, and assessments (patient POSAS and observer POSAS). After receiving the last optional high energy treatment at Visit #4, patients in this low energy treatment group will return to the clinic in 3 mos for the last study visit where pictures will be obtained, survey assessments of the scar will occur, and the

subject will exit from the study. This allows comparison of all subjects following 2 treatments, and adds further data to the high energy laser treatment group for subjects who cross over.

The subjects' participation may be up to 14 months.

Visit Flowchart

Study Visit #1

The subject will verify information regarding the subject's name and contact information. The subject cannot take part in this study if the subject has a history of prior laser treatment to the face or neck, or if

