As soon as the PI becomes aware of an AE that meets the criteria for an SAE, the SAE should be documented to the extent that information is available. A report must be submitted by the study site to the SLU IRB, within 24 hours. Forms for reporting SAEs will be provided to the study site. SAEs will be recorded from the time of informed consent, through the end of the study. If in the opinion of the Investigator, an SAE occurring outside the specified time window (i.e., following subject completion or withdrawal from the study), is deemed to be device related, then the event should be reported with 24 hours as outlined above. The Investigator should institute any clinically necessary supplementary investigation of SAE information.

Death

In the case of subject death, any post-mortem findings/reports will be requested and a report (even if a preliminary diagnosis/cause of death is available) will be submitted to the SLU IRB within 24 hours of learning about the death.

Reporting of Pregnancy

In the case of subject pregnancy, the subjects will be discontinued from the study and will be followed leading up to delivery.

Data Analysis and Statistical Considerations

At the completion of the study, the data obtained will be reviewed and analyzed with the aid of the Saint Louis University Center for Health Outcomes Research. A chi-square test along with the Wilcoxon signed rank test will be performed to assess significant difference between clinical improvement scores between study visits. There is no data to suggest that there is a difference in the appearance of older (more than 1 year old from the initial injury) and newer scars post-therapy. We will aim to recruit 20 patients with old scars (10 of which will be in the high energy treatment group, and 10 of which will be in the low energy treatment group). In terms of statistical analysis, we will review whether there is a difference between the post-treatment measurements and appearance of older scars and newer scars.

Quality Control and Quality Assurance

Quality control and assurance for this study will be performed by an internal review every 3 months to ensure that the data collected is in accordance with the goals of this study and to address any issues with data collection or performance of any study procedures.

Direct Access, Data Handling and Record Keeping

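### The randomised high- versus low-energy comparison is not prespecified: read literally, the named tests address change between visits, which in scars under one year old cannot separate a laser effect from maturation

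*Combined protocol and SAP*

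**What the plan says.** The opening summary and Dose Regimen describe random assignment to high or low energy. Blinding keeps subjects, coordinators and raters unaware of the assignment until Visit 3.

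Data Analysis and Statistical Considerations names one set of tests: a "chi-square test along with the Wilcoxon signed rank test will be performed to assess significant difference between clinical improvement scores between study visits". It describes one group contrast, without a test: "we will review whether there is a difference between the post-treatment measurements and appearance of older scars and newer scars". The clinical improvement score is not defined, and the text does not say whether arms are pooled.

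Study Objectives attaches Vectra scar length and the POSAS to the primary objective and singles out neither.

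Study Procedures says the schedule "allows comparison of all subjects following 2 treatments, and adds further data to the high energy laser treatment group" for subjects who cross over. It places the relevant assessment as follows: "Subjects will return again 3 months following the second treatment and will undergo the follow up photos and assessments". The opening summary instead has blinding hold "until the 9-month visit (Visit #3) at which time patients will be unblinded".

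On maturation, Inclusion and Exclusion Criteria states: "Most scars are fully mature at exactly 1 year from the date of the initial injury". It therefore presumes, for the older cohort, that "any changes to these scars post-therapy will be an effect from the laser". Scars of 8 to 51 weeks are also eligible. The aim is 20 older scars, 10 in each energy arm.

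**The concern.** The signed-rank test is paired and within-subject, so on visit-to-visit scores it asks whether scars changed, not whether the arms differ. A scar still maturing will change whatever the laser does. The protocol relies on this reasoning when it treats older scars as the cleaner cohort, but the analysis section does not limit the tests to them.

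Followed literally, the plan could report maturation as efficacy and leave untested the contrast that randomisation and blinding protect. With several outcomes, several raters and no named arm test, the choice of comparison would also remain open after the data are seen.

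**Working it through.** **1. Who is exposed.** 50 planned − 20 older = about 30 newer scars, if the older-scar aim is met. The figure of 50 cannot be reproduced: the plan gives no alpha, power, effect size, SD or dropout. I assume 25 per arm (10 older, 15 newer), since the overall allocation ratio is not stated, and two-sided 5% tests.

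**2. Model with no laser effect.** Change score = d × w(age) + e for newer scars and e for older scars, with e normal, SD 1. Age a is uniform on 8 to 52 weeks and follow-up lasts 26 weeks. The documents give no drift size, so d = 0.25, 0.5 and 1.0 SD of the change score are assumptions. There are three shapes for w:

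- Full: w = 1.
- Scaled to weeks left: w = min(1, (52 − a)/26). Mean w = 18/44 + ½ × 26/44 = 0.70.
- Slowest taper, with the drift rate falling linearly to zero at 52 weeks: w = [(52 − a)² − max(0, 26 − a)²]/(44² − 18²). Only an 8-week-old scar drifts in full; mean w = 0.37.

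**3. Simulated rejection rates, d = 0.25 / 0.5 / 1.0.**

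| Drift shape | Signed-rank, pooled n = 50 | Signed-rank, one arm n = 25 |
|---|---|---|
| Full | 17 / 51 / 97% | 10 / 27 / 73% |
| Scaled to weeks left | 11 / 29 / 76% | 8 / 16 / 43% |
| Slowest taper | 7 / 12 / 30% | 6 / 8 / 16% |

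On the same data the 20 older scars alone reject in about 5%, and a between-arm rank-sum test in 3–5%. The rank-sum rate falls to about 3% only at the largest drift. There, mixing scar ages equally within both arms makes the unadjusted test conservative; a linear model with arm and scar age holds about 5%.

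**4. Hand check of one cell (full drift, d = 0.5, pooled).** Mean change = 0.6 × 0.5 = 0.30. Variance = 1 + 0.6 × 0.4 × 0.25 = 1.06, so SD = 1.03. The standardised mean is 0.30 × √50 / 1.03 = 2.06. Allowing for the rank test's efficiency, 2.06 × √0.955 = 2.01. Power ≈ Φ(2.01 − 1.96) = 52%, against 51% simulated.

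**5. What the arm comparison can detect (80% power).** The normal approximation at 25 per arm is (1.96 + 0.84) × √(2/25) = 0.79 SD; the noncentral t gives 0.81 SD of the change score. At 20 per arm it is 0.91 SD. Power for 0.5 SD is 41% and 34% respectively.

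ANCOVA multiplies the 25-per-arm figure by √(1 − r²), now in units of the follow-up SD: 0.81 × 0.866 = 0.70 at baseline correlation r = 0.5, and 0.81 × 0.714 = 0.58 at r = 0.7. With equal SDs at both visits, the SD of change is √(2(1 − r)) follow-up SDs. The unadjusted 0.81 then corresponds to 0.81 follow-up SD at r = 0.5 and 0.63 at r = 0.7, so ANCOVA gains in both cases.

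**6. Time point.** Two 3-month steps give 6 months, or 26 weeks. With two windows of ±2 weeks and a first treatment up to 30 days late, the range is 22 weeks (26 − 4) to about 34 weeks (26 + 4 + 30/7). Nine months is 39 weeks.

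**The case against.** The strongest reply is that an arm comparison is plainly intended. The analysis section itself plans 10 older scars in each arm, a balance most naturally explained by comparing arms. Raters are blinded to Visit 3, and Study Procedures speaks of comparing all subjects after two treatments. The sentence on tests is garbled, and an ordinary chi-square test compares independent groups, so it may have been meant for the arms, with the signed-rank test for visits. This stands as evidence of intent: a reader might infer that the trial has no arm comparison, and the documents do not support that. But none of these places gives a contrast, outcome, time point or test.

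A reader might also infer that there is no primary outcome. That is too strong: outcomes are attached to the primary objective, and the gap is that none is singled out.

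On maturation, the protocol credits change to the laser only in the older cohort and plans an older-versus-newer review. That is a partial safeguard. It would be too strong to say that the protocol claims all change as laser effect, or that the older-scar results are inflated by maturation.

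The rates in the table rest on assumed drift and run from 6% to 97%. Pooling is not stated, so the per-arm column matters as much as the pooled one, and under the slowest taper at 0.25–0.5 SD the per-arm inflation is small.

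Finally, Study Procedures says that subjects "will have the segment of the scar with the most deformity defined for objective evaluation at each session", which might suggest regression to the mean. That is not established: the documents do not say that this choice and the baseline score share one rating.

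**Conclusion.** The point holds as a gap in the analysis plan, not in the design. The trial can support a valid comparison of high with low energy; the plan does not state one. As literally written, its tests have no concurrent control, and about 30 of 50 subjects have scars in which change may be maturation.

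The absence of a control does not depend on the simulation. The size of the error does: it depends on the drift size, the taper and whether arms are pooled, and the documents fix none of these. The rates are illustrations, not estimates of this trial's error rate. The detectable differences likewise assume 25 per arm and the stated correlations.

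**What to change.** State in Data Analysis and Statistical Considerations that:

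- the primary efficacy analysis compares high with low energy, subjects analysed as randomised, at Visit 3 and before any treatment given at that visit;
- it uses one outcome chosen in advance from Study Objectives, with the rater named;
- the method is ANCOVA adjusted for baseline and scar-age group or, at minimum, a rank-sum test on change;
- between-visit tests are secondary within-arm summaries that do not alone support an efficacy claim;
- the ordinary chi-square test is not applied to paired visits;
- data after crossover stay out of the arm comparison.

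The Visit 3 timing in the opening summary must be reconciled with Study Procedures and Study Visit #3, so that the comparison has one time point.

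This costs wording only: no added visits, data or subjects. The scientific cost is real. Both arms receive laser, so the conclusion becomes high versus low energy, which is narrower than the stated objective and could be null if both energies work. With 50 subjects, only a fairly large difference is likely to be detected.

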The primary objective is to assess the efficacy of fractionated carbon dioxide laser in improving surgical scars. Objective assessment of the scars will involve the Vectra microtopographic imaging system to measure changes in the length of the scar. The Patient and Observer Scar Assessment Scale (POSAS) is a validated survey that will be utilized for subjective assessments of the vascularity, pigmentation, thickness, pliability, surface area, relief, pain, and pruritus.

The secondary objective will be to evaluate the tolerability of the laser, by assessing the severity and duration of known side effects of laser therapy such as erythema, edema, burning sensation, post-inflammatory pigment changes, infection, scarring, xerosis, pruritus, bronzing, and any other adverse events that arise following treatment. Patients will be given a 30-diary after each treatment to document this information.

Selection and Withdrawal of Study Subjects

Study Population

The study population will consist of 50 adult patients 18 years of age or older with surgical scars located on the head and neck.

Minors are not included due to the Mohs patient population being adults only who have undergone surgical excisions of skin cancers on the head or neck. Although participants are not

required to be patients in the Mohs clinic, scars and healing may be significantly different in children, making the data less reliable and difficult to interpret.

Inclusion and Exclusion Criteria

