This fractionated ablative laser is FDA approved for the revision of surgical scars. Access to this laser may also be obtained outside of the study.

Mechanism of Action

The 10,600 nm carbon dioxide (CO2) laser utilizes high energy at short durations to vaporize intra- and extra-cellular water, resulting in tissue ablation causing a substantial thermal injury to the dermis, reducing the likelihood of additional scarring (Chapas, 2008). The incorporation of fractional photothermolysis, first introduced by Manstein et, al. facilitates a controlled area of dermal injury creating cylindrical microscopic treatment zones (MTZ) of necrosis (Hong Li, 2010, Manstein et al, 2004). Sparing uninvolved normal healthy tissue, each wound is surrounded by healthy cells that can migrate towards the wound, allowing for faster healing by secondary intention (Manstein et al, 2004). The fractionated CO2 laser is selective in that segments of tissue are effected, which translates into decreased recovery time (downtime) for the patient (Bordenorf, 2009). Therefore, by causing selective thermal injury in the skin, the CO2 laser can stimulate collagen production and theoretically improve scar thickness, pliability, and texture.

Dose Regimen

Subjects will be randomized to either a high energy treatment (CO_2RE Mid treatment mode [45-257 mJ] or CO_2RE Deep treatment [30-70 mJ] mode) or a low energy treatment (CO_2RE Light treatment mode [18-74.5 mJ] mode).

Study Device: Canfield Vectra M3 Imaging System

This body imaging is utilized in several clinical trials to capture 3-D photographs of subjects. Subjects will have images and dimensions of their scars measured in a non-invasive manner at each visit using photographs taken with the Canfield Vectra M3 3D Body Imaging System. Detailed step-by-step instructions for executing the images and measuring the scars will be a separate document.

Study Procedures

[figure not shown]

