the subject tends to form keloid scars or scars from minor trauma. Also, the subject should not participate in the study if the subject has taken oral isotretinoin medication within the past 6 months. In addition, the principle investigator may exclude the subject from the study if she determines that the study may put the subject at risk. The subject will provide written consent (permission) to be a participant in the study and for the research team to access the subject's health information to learn more about the surgery that resulted in the scar and the original features of the scar. Immediately before any study visit, the subject will be asked to not wear any make-up or use facial moisturizers (or moisturizers on the neck). The subject will be asked to cleanse their face with a gentle cleanser, such as Cetaphil, provided in the office prior to treatment.

Other procedures at this visit:

- The subject will have photographs taken of the scar that will be shared confidentially with two other research physicians in the study for them to answer questions about the scar.
- The subject will complete a questionnaire about the scar and another research physician will see the subject at this visit to evaluate the scar.

If the subject qualify for study treatment the following may occur at the same visit or at a return visit within 30 days. The following will occur:

- If the subject has a history of recurrent fever blisters/cold sores on the lips or face, The subject will be offered a three day prescription for an antiviral medication that the subject can fill at the subject's pharmacy to prevent a recurrence since laser treatments may increase the chance of recurrent episodes. The subject would take one pill every twelve hours the day prior to treatment, on the treatment day, and the first day post-treatment. The subject or their insurance plan must cover the cost of the medication. This may delay the treatment to a later date within 30 days of the screening visit.
- The subject will complete a pre-treatment questionnaire.
- The subject will receive laser treatment as randomized to either high energy or low energy treatment which includes:
 - Prior to treatment, the subject will be asked to cleanse his or her face with a gentle cleanser, such as Cetaphil, provided in the office in order to remove all lotion, creams, make up, and sunscreen.

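### The analysis section names no test of high versus low energy and no use of the pre-treatment POSAS and Vectra values as covariates; a Visit 3 ANCOVA would supply both

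*Combined protocol and SAP*

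**What the plan says.** The efficacy analysis is contained in the Data Analysis and Statistical Considerations section. Its one sentence on methods says that, along with a chi-square test, "the Wilcoxon signed rank test will be performed to assess significant difference between clinical improvement scores between study visits". The section does not define the improvement score or say what the chi-square test tabulates. It adds that "we will review whether there is a difference between the post-treatment measurements and appearance of older scars and newer scars", which refers to post-treatment values and does not mention baseline. No test of high against low energy is named, and no covariate appears.

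Pre-treatment values are collected. The opening summary says that at study visits "the scars will be photographed pre-treatment and the subject will complete a questionnaire to rate the scar". Study Procedures, on the screening visit, states "Baseline photographs of this area will be obtained". Study Visit #1 adds "The subject will complete a questionnaire about the scar and another research physician will see the subject at this visit to evaluate the scar". The Canfield Vectra section provides for "images and dimensions of their scars measured in a non-invasive manner at each visit", and the objectives use that system to "measure changes in the length of the scar".

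Study Procedures explains that the visit schedule lets all subjects be compared after two treatments. Visit 3 falls three months after the second treatment. Unblinding and the optional high energy treatments take place at that visit.

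**The concern.** Subjects are randomised between two energy levels, so the result that randomisation protects is the difference between arms. A signed rank test between visits asks whether scars changed within patients. Scars can change over time in both arms, so a positive result does not show that one energy level works better than the other.

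An arm comparison will have to be added, and the plan does not say how baseline will enter it. Since the only named method that plausibly uses baseline is a paired difference, the obvious extension is to compare raw change between arms. That is less precise than adjusting for baseline, which matters with 50 subjects. Eligible scars range from 8 weeks old with no upper limit, and the randomisation section describes no stratification by severity. A chance difference in starting severity between arms is therefore quite possible.

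**Working it through.** **The plan's own figure.** The documents give 50 subjects. They give no alpha, power, effect size, SD or correlation, so 50 cannot be reproduced. For context, 25 per arm at two-sided 5% and 80% power detects about 0.79 SD without adjustment: (1.96 + 0.84) × √(2/25) = 0.79.

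**Assumed inputs.** 25 per arm (the documents state an equal split only for the 20 older scars), two-sided 5%, no dropout, outcome SD of 1 at both visits, true arm difference 0.6 SD. The correlation rho between baseline and Visit 3 runs from 0.3 to 0.9.

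**Variance per subject.**
- Raw change: 2(1 − rho)
- Baseline-adjusted: 1 − rho²
- Ratio, adjusted to change: (1 + rho)/2, which does not exceed 1

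Estimating the slope multiplies the adjusted variance by about 1 + 1/(50 − 4) = 1.022 and leaves 47 rather than 48 degrees of freedom.

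**Power.** Non-central t with non-centrality 0.6/√(variance × 2/25). At rho 0.5 this is 0.6/√(1.00 × 0.08) = 2.12 for change and 0.6/√(0.75 × 1.022 × 0.08) = 2.42 after adjustment.

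| rho | Variance: change | Variance: adjusted | Power: change | Power: adjusted, before slope cost | Power: adjusted, after slope cost | Net gain (points) |
|---|---|---|---|---|---|---|
| 0.3 | 1.40 | 0.91 | 42.0% | 58.7% | 57.7% | about 16 |
| 0.5 | 1.00 | 0.75 | 54.7% | 67.0% | 66.0% | about 11 |
| 0.7 | 0.60 | 0.51 | 76.5% | 82.9% | 82.1% | about 6 |
| 0.8 | 0.40 | 0.36 | 90.8% | 93.4% | 92.9% | about 2 |
| 0.9 | 0.20 | 0.19 | 99.6% | 99.8% | 99.7% | about 0.1 |

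At rho 0.5, 50 subjects analysed with adjustment carry about the information of 50/0.75 = 67 analysed by change, before the slope cost. A second covariate unrelated to outcome (factor 1 + 2/45, 46 degrees of freedom) would take about one further point at rho 0.5, to 65.0%.

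**Simulation (3,000 runs, same assumptions).** A rank-sum test on change, closer to the plan's nonparametric style, had 51% power against 66% for ANCOVA at rho 0.5, and 74% against 82% at rho 0.7.

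**What the signed rank test answers.** When both arms improved by 0.6 SD and did not differ, the signed rank test within one arm rejected in 81% of runs at rho 0.5 and 95% at rho 0.7. A between-arm rank-sum test on change rejected in about 5%.

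**Chance imbalance.** The baseline difference between arms has SD √(2/25) = 0.28, so a gap above 0.3 SD either way occurs in about 29% of such trials. Given a gap of 0.3 SD at rho 0.5, the change-score contrast shifts by (1 − 0.5) × 0.3 = 0.15 SD, in favour of the arm that started with worse scars.

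**The case against.** The strongest objection is that the comparator is not in the plan. A reader might infer that the plan forfeits the power shown above. The documents do not support that, because they name no between-arm test on change scores and so plan no arm estimate that could lose precision. This stands. The figures compare two ways of filling a gap, and the gap itself is the larger defect.

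A reader might also infer that every planned test uses baseline only as one half of a visit-to-visit difference. That fits the signed rank test alone. The chi-square input is unstated, the improvement score is undefined, and the older-versus-newer review mentions no baseline.

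Nor would change scores bias the result in general: over repeated randomisation they are unbiased. The distortion is conditional on an imbalance that has actually occurred.

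Two further limits stand. The gain depends on a correlation that the documents do not give. The protocol re-evaluates one defined scar segment, so length may be very highly correlated between visits and gain almost nothing. In addition, the sentence about comparing all subjects after two treatments names neither Visit 3 nor a method, and it goes on to mention extra high energy data from crossover subjects. It supports the intent to compare, but the randomised contrast without optional treatment is available only at Visit 3 before that treatment.

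Finally, ANCOVA on several measures does not settle which outcome is primary or how multiplicity is handled. Those decisions are still needed.

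**Conclusion.** The point holds in a limited form. The analysis section specifies neither a test of the randomised arms nor covariate use of the pre-treatment values that the trial collects. The signed rank test cannot fill the first gap. For the second, baseline adjustment beats raw change except for the small cost of estimating a slope. The net gain is material at moderate correlations (about 11 points at rho 0.5) and minor at 0.8 and above. These sizes rest on the assumed 25:25 split, two-sided 5%, 0.6 SD difference and equal variances. They illustrate the choice of method and do not measure power lost by a planned analysis. The change is worth making because it is nearly free and also supplies the missing arm comparison.

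**What to change.** In Data Analysis and Statistical Considerations, state that the randomised arms will be compared at Visit 3, before any optional treatment. Use ANCOVA on each continuous POSAS score and Vectra measure. The covariates are randomised arm, the subject's own last value of that measure before the first treatment, and scar-age group (8–51 weeks versus 52 weeks or older). Specifying the last pre-treatment value settles which rating counts when the first treatment is deferred by up to 30 days and the questionnaire is completed again.

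Report the adjusted arm difference with its 95% confidence interval. Use a rank-based ANCOVA as a sensitivity analysis, and keep the signed rank tests as descriptive summaries of within-arm change.

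The cost is a change of wording, two degrees of freedom and a little more analysis work. No new data or visits are required.
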